6.4 Data minimisation			
Only the essential baseline characteristics and data, that are required to answer the research question, will be collected:	Yes 		No 
6.5 Statistical and/or qualitative analysis			
Please specify Statistical Analysis Plan (SAP): a. Description of study population: The study population consists of nursing newcomers who are already enrolled or will enrol in the fast-track integration trajectory at UMCG and participating partner hospitals. This includes both asylum seekers and migrants. Demographic and baseline characteristics include age,			

gender, language proficiency, participant status (asylum seeker or migrant), and socioeconomic and employment background. Participants who provide consent for research purposes will be included in the analysis.

b. Description of preparation of the data for analyses:

Collected data will be pseudonymized and direct identifiers removed. Data cleaning will involve checking for completeness, consistency, and plausibility. Variables will be coded according to pre-specified categories (e.g. employment history, language level). Missing data will be handled using appropriate methods such as multiple imputation or sensitivity analyses, depending on the extent and pattern of missingness. For qualitative data from surveys or interviews, responses will be anonymized and transcribed for coding and thematic analysis.

c. Specify all applicable statistical and/ or qualitative methods. This usually requires an extensive description of the planned analyses and covariates:

Primary outcome analysis: Descriptive statistics and inferential analyses (e.g. proportions, means, standard deviations) will be calculated for successful trajectory completion, BIG registration achievement. Associations with baseline characteristics will be explored using logistic regression or other appropriate multivariable models.

Secondary outcome analysis: Qualitative data from the Regioplan survey will be analyzed using thematic analysis to identify patterns, facilitators, and barriers in the trajectory. Quantitative secondary measures (e.g. language progress, employment outcomes) will be summarized using descriptive statistics and, where appropriate, tested with regression models to explore predictors of success.

Subgroup analyses will consider variables such as asylum seeker vs. migrant status, age groups, gender, and baseline language proficiency.

d. Clarify how this analysis plan, study setup, sample size and design will answer the study questions:

This analysis plan ensures that both primary and secondary outcomes are systematically evaluated. The prospective cohort design, together with a projected sample size of approximately 300 participants nationwide (80 in the Northern region), allows for sufficient statistical power to explore patterns of trajectory completion and integration success.

Qualitative analyses complement the quantitative results by providing in-depth understanding of barriers, facilitators, and contextual factors affecting trajectory outcomes. Together, these analyses will answer the research questions regarding the effectiveness, scalability, and potential optimization of the integration trajectory for nursing newcomers.

Has the statistical analysis section (6.5) been completed?

Yes

No

7. Recruitment and informed consent/objection

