This study can be considered both a pilot and an exploratory study for several reasons. First, the program under investigation was not originally conceived as a research project but as an improvement initiative, meaning that the data were collected prospectively in a real-world setting without predefined hypotheses. Second, the number of participants is still limited, and the program is in an early stage of implementation across centers, which makes the findings preliminary by nature. Third, the primary aim is descriptive, examining proportions of participants who progress through or complete different phases of the program, rather than testing causal relationships. In addition, secondary analyses, such as the societal business case and the qualitative assessment of program impact, are exploratory in character, intended to generate insights and hypotheses for future, more definitive evaluations. Taken together, these features justify the classification of the study as a pilot and exploratory investigation, providing essential groundwork for larger-scale, hypothesis-driven research.

In case of a pilot study, what are the concrete follow-up plans.

The concrete follow-up plan is to expand the program to hospitals at the national level and to integrate data from these additional sites into the analysis. This will allow for larger-scale evaluation, validation of findings across different contexts, and the development of more robust evidence on program effectiveness. Ultimately, the pilot provides the foundation for a nationwide multicenter study aimed at informing sustainable policy and implementation.

5. Population

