Have all the data for the primary and secondary outcomes been described or the alternatives?	Yes 	No 	
6.2 Number of participants: Target total number of participants is estimated to fall within the range: 159-227 Target number of UMCG participants is estimated to fall within the range: 118-147			
6.3 Justification of sample size Based on the observed enrolment rates in the Northern region (3.3 participants per hospital per year) an additional 98 participants are expected to enrol between March 2025 and March 2031 if the 5 hospitals in this region continue to participate. Assuming a similar rate of enrolment in the Randstad, an additional 80 participants are expected in this period across the 4 hospitals located there. This results in a maximum of 227 participants across all hospitals during the entire study period. However, given potential risks such as hospitals discontinuing their participation due to lack of financial resources to cover 4–6 months of above-budget salary costs, a more conservative projection of approximately 30% fewer participants should be considered resulting in an estimated range of 159–227 participants. The sample size is therefore not based on a formal power analysis but on realistic projections of expected enrolment, as no official national data on the number of nursing newcomers are available. As such, the study follows a pragmatic design in which all eligible participants can enroll, depending on the availability of places in the hospitals involved in their region. This ensures that the sample is sufficiently large to answer the research questions regarding integration success, retention, and professional registration outcomes, while at the same time adhering to GDPR requirements to not include more participants than necessary.			
Has the sample size justification been described?	NA 	Yes 	No 

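### Section 6.5d justifies the design with about 300 participants (80 in the North) and adequate power, but sections 6.2 and 6.3 project at most 227 in total, 98 further participants in the North alone, and no power analysis

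*Protocol*

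**What the plan says.** Section 6.5d, which explains how sample size and design answer the study questions, states that "a projected sample size of approximately 300 participants nationwide (80 in the Northern region), allows for sufficient statistical power" to explore patterns of completion and integration success.

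Section 6.2 gives different numbers: "Target total number of participants is estimated to fall within the range: 159-227", and "Target number of UMCG participants is estimated to fall within the range: 118-147".

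Section 6.3 explains the total. It starts from an observed Northern rate of 3.3 participants per hospital per year. From March 2025 to March 2031 it expects 98 more participants in five Northern hospitals and 80 more in four Randstad hospitals. It concludes: "This results in a maximum of 227 participants across all hospitals during the entire study period". A reduction of about 30% then gives the lower bound of 159. On the basis for the size it says: "The sample size is therefore not based on a formal power analysis".

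Section 7.2.2.2 reports 49 participants already enrolled. Section 4.5 describes a pilot and exploratory study without predefined hypotheses and with a descriptive primary aim.

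**The concern.** One protocol gives two sample sizes for the same study, and the larger one supports the statement that the study is big enough. That larger figure exceeds what the enrolment section calls the maximum, and its regional split does not match that section either. The power statement sits beside a section that says no power analysis was done.

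A reader or ethics committee cannot tell which size governs. Section 6.3 also invokes the data-protection duty not to include more participants than needed, which presupposes one consistent number. Anyone relying on 6.5d would expect more information from comparisons within the cohort than the projected enrolment can give.

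**Working it through.** **Inputs.** Rate 3.3 per hospital per year; 5 Northern and 4 Randstad hospitals; 6 years; 98 and 80 further participants; reduction of about 30% (all 6.3). Already enrolled: 49 (7.2.2.2). Claimed size: 300, with 80 in the North (6.5d).

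**Step 1: reproduce 6.3.**
- North: 3.3 × 5 × 6 = 99, against 98 stated.
- Randstad: 3.3 × 4 × 6 = 79.2, against 80 stated.
- Total: 49 + 98 + 80 = 227, as stated.
- Lower bound: 0.7 × 227 = 158.9, or 159, as stated.

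Section 6.3 is therefore coherent with the 49 in 7.2.2.2.

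**Step 2: compare the total in 6.5d.** 300 − 227 = 73 participants. 300/227 = 1.32 and 300/159 = 1.89. The projection inputs in 6.3 and 7.2.2.2 do not lead to 300.

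**Step 3: compare the North.** The 98 further Northern participants already exceed 80. Section 6.3 prints no Northern total. If all 49 already enrolled are Northern (an assumption), the maximum is 49 + 98 = 147, and the Northern share is 147/227 = 65%, against 80/300 = 27% in 6.5d. With the 30% reduction the North is 0.7 × 147 = 102.9 or, if only future enrolment is reduced, 49 + 0.7 × 98 = 117.6. Both exceed 80. Without the assumption, the reduced future enrolment alone is 0.7 × 98 = 68.6, so 80 would be passed once 12 of the 49 are Northern.

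**Step 4: the UMCG range in 6.2.** Its upper end, 147, equals 49 + 98, the sum for all five Northern hospitals. Its lower end, 118, matches 49 + 0.7 × 98 = 117.6. The overall lower bound of 159 instead takes 30% off everyone, including those already enrolled. Reducing only future enrolment would give 49 + 0.7 × 178 = 173.6, or 174.

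**Step 5: precision of the primary proportion.** Half-width = 1.96 × √(p(1 − p)/N). The protocol gives no expected proportion, so p is assumed:

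| N | p = 0.8 | p = 0.5 |
|---|---|---|
| 300 | 4.5 points | 5.7 points |
| 227 | 5.2 points | 6.5 points |
| 159 | 6.2 points | 7.8 points |

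For example, at N = 227 and p = 0.5: 1.96 × √(0.25/227) = 0.065.

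**Step 6: power, as illustration only.** The protocol's claim cannot be reproduced, because it states no comparison, error rate, effect or proportion. Assume two equal subgroups and a two-sided 5% test. With h = 2·asin√p₁ − 2·asin√p₂, power = Φ(h√(N/4) − 1.96).
- 75% against 60%: h = 0.322; power 80% at N = 300, 68% at 227, 53% at 159.
- 85% against 70%: h = 0.364; power 88%, 78% and 63%.

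An unpooled normal approximation agrees within about one point. Unequal subgroups would have less power.

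**The case against.** The strongest reply is that little depends on the 300. All eligible participants may enrol as places allow, so no recruitment target or stopping point is tied to it. Reported intervals will use the actual number, and the loss of precision for the primary proportion is about 2 points at most. The power sentence is also qualified: it speaks of power to explore. All of this stands and limits the severity. It does not reconcile the numbers or give the power claim a basis.

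National expansion might be offered as the source of 300. Section 4.5 presents that as a follow-up plan, while 6.3 already includes the Randstad hospitals and sets 227 as the maximum for the entire study period. Expansion also cannot explain a Northern figure below 98. Power details could sit in a separate analysis plan, but the issue is two conflicting printed statements, not an omission.

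A reader might infer more than the protocol supports:
- **Retention.** Section 6.3 calls the sample adequate for retention, and one might think the data stop at exit. Section 6.1 records dropout, its date and phase, on-track status and the start date as a qualified nurse, so retention in the programme is measured. Nothing in 6.3 says that it means employment after exit.
- **Effectiveness.** The next paragraph of 6.5d says "these analyses will answer the research questions regarding the effectiveness, scalability, and potential optimization". One might read this as a causal claim that a cohort without a comparator cannot support. Section 4.5 states that the aim is descriptive, "rather than testing causal relationships", and leaves firmer evidence on effectiveness to the follow-up. This is at most loose wording and is separate from the sample size.
- **Unlabelled subgroup and regression analyses.** Section 4.5 classes the study as exploratory, and 6.5c says that associations and predictors will be explored. Section 6.5d does not tie its power claim to any named subgroup or regression analysis.

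**Conclusion.** The contradiction holds on the protocol's own text. The 300 is 32% above the stated maximum and 89% above the lower projection. The Northern 80 is below the further Northern enrolment expected at full projection and coincides with the Randstad figure. A mix-up of regions is possible but cannot be confirmed. The power claim has no stated basis and conflicts with 6.3.

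These conclusions need no outside assumption. Three other figures do: 147 as the Northern maximum assumes that all 49 already enrolled are Northern, the half-widths assume success of 50% to 80%, and the power figures assume equal subgroups and the proportions shown.

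This should be fixed, but it does not undermine the primary analysis, because that analysis is descriptive and enrolment does not depend on 300.

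**What to change.** In 6.5d, replace 300 and 80 with the figures from 6.2 and 6.3: 159 to 227 in total and up to 147 in the North, stating that the latter counts all 49 already enrolled as Northern, if that is so.

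Delete the power claim. State instead the expected precision of the primary proportion: a 95% half-width of about 5.2 to 6.5 points at 227 and 6.2 to 7.8 points at 159, for assumed success of 80% to 50%. If the sponsor prefers to keep a power statement, it should give the comparison, error rate, assumed proportions and resulting power at 159 and 227.

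In 6.2, reconcile the range labelled as UMCG participants with the five-hospital sum that it matches, and apply one rule for the 30% reduction to both lower bounds.

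The cost is wording only. No data collection or design feature changes, although the stated figures become less favourable.

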3.1 Introduction and rationale

The increasing shortage of nurses in the Netherlands significantly impacts healthcare capacity¹. Currently, half of all job vacancies in the Netherlands are in healthcare, trade, and business services². Reports indicate that nursing faces the largest labor market shortages among the healthcare professions, with 10,500 vacancies in 2021 and an expected 24,900 by 2031^{3,4}. Enhancing personnel inflow is one of the solutions. In that regard, the Dutch system does not appear to be well-equipped to support the integration of refugees and migrants certified as nurses in their country of origin, into healthcare positions. Recognition of qualifications is characterized by long delays and there is a lack of guidance^{5,6}. In practice, it also takes a considerable amount of time to reach a sufficient level of language proficiency, especially if individuals are unable to work and have limited exposure to the Dutch language. This slows down the speed at which the tests for obtaining a declaration of professional competence, required for Dutch healthcare licensure, are completed. Consequently, many qualified newcomers in healthcare are either underemployed or unemployed⁵. In 2022, the UMCG assessed the interest among nursing newcomer in the Northern region to participate in a fast-track integration programme (Appendix 1). As sufficient interest was confirmed, such a programme was developed that includes a vocational language and intercultural communication course, after which participants begin working as assistant nurses, salaried as care assistants, while receiving guidance toward BIG registration before taking the examinations required for BIG registration (appendix 2). In this process, data were prospectively collected on whether the participating newcomers successfully completed the different phases of the program, the duration of these phases, and the stage of integration and employment situation from which they entered, and consent was obtained from participants to store these data (appendix 3). The programme was initially developed at the UMCG and grew into a multicentre initiative. In collaboration with Healthcare of the North ('Zorg voor het Noorden', ZvhN), a regional network across the three northern provinces, it has expanded to four non-academic hospitals. As this improvement process, which was not initially conceived as a research project, appeared to be successful, it was subsequently decided to analyze the outcomes in a scientific manner. The primary objective is to determine the proportion of participants who are either progressing as planned or successfully completed the program. In addition, a qualitative analysis and a societal business case is conducted to identify where the benefits lie, thereby providing guidance for sustainable implementation once philanthropic funding is phased out. Additionally, the study aims to analyze potential racial microaggression in the workplace.

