5.4 Inclusion and exclusion criteria

- Inclusion criteria:

- refugee or migrant with a nursing background or other paramedical background and sufficient indications that the relevant hospital department is prepared to cooperate in a fast-track integration trajectory
- holding at least a diploma equivalent to the Dutch MBO-4 level
- having practical experience, preferably in a hospital setting
- residence in one of the three northern provinces
- sufficient learning capacity to participate in a language course at the University of Groningen's Language Centre (LC) based on the intake and, if available, a study skills test
- a successful application interview

- Exclusion criteria:

- diploma lower than Dutch MBO-4 level
- refugee or migrant with a background as medical doctor

6. Study data, and analysis

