- Income level (if employed): 1 Less than or equal to minimum wage; 2 Comparable to a healthcare assistant's income; 3 Higher than a healthcare assistant's income
- Receiving healthcare allowance: 1 Yes; 2 No
- At entry EuroQol EQ-5D-5L questionnaire
- At exit EuroQol EQ-5D-5L questionnaire
- Residence and work permit for the Netherlands
- Basis for a residence permit? asylum; residence with partner; study (temporary residence permit); other

- Have you already had a 'Further Hearing' with the IND?
- Completed language/integration course?
- English/ Dutch language proficiency level: 1 A2 to B1; 2 B1 to B2; 3 B2
- Initials, surname, age, email address, phonenumber, current address or name of the shelter
- Domains: self-efficacy (resilience, flexibility, and adaptability; motivation and self-awareness; curiosity and lifelong learning; reliability and attention to detail); working with others (empathy and active listening; leadership and social influence); Ethics (cultural competence); physical skills (manual dexterity, endurance, and precision in the professional field); management skills (quality control); technological literacy (Appendix 4)
- Modified Racial Microaggressions Scale (RMAS) including 6 subscales: invisibility, criminality, dysfunctional culture, sexualization, foreigner/not belonging and environmental microaggressions. This questionnaire was developed by Torres-Harding et al⁸ and modified by King et al⁹ and appears to be an appropriate tool to assess this on the workplace¹⁰ (appendix 6).

Data to be completed by language center:

- Suitable candidate for 'Newcomers in Their Strength 2.0' program (based on intake)? No, the candidate is definitely unsuitable; yes, this is a suitable candidate; there is doubt about the candidate's suitability
- Score Study Skills Test
- Optional 2nd Score Study Skills Test
- Reason for taking 2nd Study Skills Test?

Data to be completed by study coordinator:

- Is the candidate a refugee or asylum seeker?
- Date of introductory meeting
- Candidate enrolled in newcomers program? no; yes; no, but may be considered in the future if the candidate develops appropriately

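### Section 6.5d promises an answer on the programme's effectiveness, but a single cohort of selected, consenting enrollees with no comparator can only describe outcomes among entrants

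*Protocol*

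**What the plan says.** Section 6.5d, which explains how the plan answers the study questions, closes with: "Together, these analyses will answer the research questions regarding the effectiveness, scalability, and potential optimization of the integration trajectory for nursing newcomers".

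The rest of the protocol describes something narrower.

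- **Questions (3.3).** The primary question asks what proportion progress as planned or complete the programme at 3, 6 and 10 years. The others concern the business case and qualitative impact, competencies and the need for support, and microaggressions. None asks how participants fare against any alternative.
- **Aim (4.5).** "the primary aim is descriptive, examining proportions of participants who progress through or complete different phases of the program, rather than testing causal relationships". The same section treats firmer evidence on effectiveness as a product of the planned national expansion.
- **Population (6.5a).** "The study population consists of nursing newcomers who are already enrolled or will enrol in the fast-track integration trajectory at UMCG and participating partner hospitals". Only those who consent to research use are analysed.
- **Entry (3.2, 5.4).** Entrants need a diploma at MBO-4 level or above, practical experience, "sufficient learning capacity to participate in a language course", a successful interview and indications that a department will cooperate. The language intake weighs motivation, initiative, intelligence and communication skills.
- **Deferral (6.1).** One recorded field reads "Candidate enrolled in newcomers program? no; yes; no, but may be considered in the future if the candidate develops appropriately".
- **Analyses (6.5c).** Descriptive statistics, regression on baseline characteristics within the cohort, subgroups and thematic analysis.

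**The concern.** Effectiveness normally means the difference between what participants achieved and what the same people would have achieved without the programme. The protocol plans to observe only the first of these.

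Entry criteria that favour learning capacity, motivation and a good interview plausibly favour success with or without the programme. Candidates who are not ready can be deferred until they are. Section 3.1 describes the ordinary route as slow: "it also takes a considerable amount of time to reach a sufficient level of language proficiency". That sentence goes on to say that this applies especially to people who cannot work and have little exposure to Dutch. It therefore supports a delayed ordinary route, and it gives no figure for how many would finish it.

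What is at stake is how the result will be read. Section 3.1 intends the business case to guide implementation once philanthropic funding is phased out, and 4.5 plans national expansion. A high proportion presented as an answer on effectiveness would enter those decisions as evidence that the programme causes success, which the design cannot show.

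**Working it through.** **1. The plan's own sample size.** Inputs are from 6.3, plus the 49 already enrolled from 7.2.2.

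- North: 3.3 × 5 hospitals × 6 years = 99 (stated 98).
- Randstad: 3.3 × 4 × 6 = 79.2 (stated 80).
- Maximum: 49 + 98 + 80 = 227.
- With 30% fewer: 227 × 0.70 = 158.9, or 159.

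The stated range of 159 to 227 reproduces. It is an enrolment projection: 6.3 says no formal power analysis was done, and there is no reference rate to test against. Section 6.5d gives a different total, about 300. That discrepancy is a separate matter, and the argument below does not depend on it.

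**2. What the cohort can estimate.** The 95% half-width for one proportion is 1.96 × √(p(1 − p)/n). The values of p are assumptions.

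| n | p = 0.50 | p = 0.80 | p = 0.90 |
|---|---|---|---|
| 159 | 7.8 points | 6.2 points | 4.7 points |
| 227 | 6.5 points | 5.2 points | 3.9 points |
| 300 | 5.7 points | 4.5 points | 3.4 points |

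This is useful precision for a descriptive aim.

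**3. What it cannot estimate.** Let S be the proportion succeeding in the programme, and c the proportion of the same selected people who would have succeeded without it by the same time. The effect on that proportion is S − c. The protocol gives no value for c and plans no data on it. Taking S = 0.80 purely for illustration:

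| Assumed c | S − c |
|---|---|
| 0.20 | 60 points |
| 0.40 | 40 points |
| 0.60 | 20 points |
| 0.80 | 0 points |

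These rows are the same at n = 159, 227 or 300. A larger cohort narrows the interval around S and says nothing about c.

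**4. Whether the planned analyses fill the gap.**

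- Regression on baseline characteristics compares enrollees with one another. All of them are exposed, so it yields predictors of success among entrants, not a programme effect.
- The confounder list in 3.2 does not change this, because there is no exposure contrast to adjust.
- Section 6.1 records reasons for rejection, but no outcome follow-up of rejected candidates is planned, so they cannot serve as a comparison.

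**5. The text side by side.** Section 6.5d refers to research questions on effectiveness; 3.3 contains none. Section 4.5 disclaims causal testing and defers effectiveness; 6.5d says this study will answer it.

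**The case against.** The strongest reply is that the protocol already contains the needed disclaimer. Section 4.5 calls the work exploratory and its findings preliminary, 6.5c plans no effect estimate, and effectiveness in 6.5d may be loose wording for completion. Eligibility criteria are also no flaw in themselves: a proportion among eligible entrants is a legitimate descriptive target. All of this stands, and it limits the point to what 6.5d claims. It does not remove the point, because 6.5d does not define the word that way and 4.5 uses it for evidence still to come.

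A reader might infer more: that every success, and every change in EQ-5D-5L from entry to exit, would be credited to the programme, or that the business case is overstated by some definite factor. The documents do not support either inference.

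- Section 6.1 lists EQ-5D-5L at entry and exit as data items; no section says how the change will be analysed or attributed.
- The cost-benefit analysis was commissioned externally (8.4) and its method is not shown. It may contain its own no-programme scenario.
- Any overstatement factor would follow entirely from the values chosen for S and c. It would also misjudge a fast-track programme: someone who would have registered eventually still gains from registering sooner, and S − c counts that gain as nothing.

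A practical objection also stands in part. The first questionnaire asked consent for storage of at most one year (Appendix 3), so early records of people who never enrolled may no longer be available.

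**Conclusion.** The point holds as a wrong claim in 6.5d that conflicts with 3.3 and 4.5. The study can report the proportion succeeding among selected, consenting entrants, with a half-width of about 4 to 8 points at the projected sample size, and can explore predictors among them. It cannot estimate a programme effect at any sample size.

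This conclusion rests on the text and on the absence of any comparator or reference rate in the protocol. The success proportions used above are assumptions, and the conclusion does not depend on them. The size of any gap between the observed proportion and a true effect cannot be derived from the documents, so none is claimed. The descriptive, scalability and optimisation aims are not undermined, and no control group is called for.

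**What to change.** 1. **Reword 6.5d.** Replace effectiveness with a descriptive aim: completion, duration and predictors of success among selected entrants. State that no causal claim about the programme is made. This brings 6.5d into line with 3.3 and 4.5.
2. **Report the selection flow.** Beside the primary proportion, give aggregate counts of people registered, rejected (by reason), deferred, enrolled and consenting. The enrolment and rejection fields are already in 6.1, and 7.2.2 already provides for recording how many decline consent. Where storage consent has lapsed for early registrants, say so and give the period the counts cover.
3. **Business case.** Wherever it attributes benefit to the programme, state the no-programme assumption and vary it over a justified range, counting earlier registration as well as eventual registration.

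The cost is a sentence or two of text, one table from fields already listed and one sensitivity analysis. No new data collection is needed. The flow table may be incomplete for the earliest period. The downside is a less favourable headline claim.
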